11.0 Treatment Evaluation

11.1 Terms and definitions

Serum or urine M spike of any level is not a requirement for entry into the study. If present, and meets criteria for measurable disease this will be followed for M protein response using IMWG uniform response criteria as described below.

Definitions for EMD response is similar to those used for patients with lymphoma (Cheson et al. Revised Response Criteria for Malignant Lymphoma). EMD measurements should be taken from the CT portion of the PET/CT, or MRI scans, or dedicated CT scans where applicable. For patients with only skin involvement, skin lesions should be measured with a ruler. Measurement of tumor size will be determined by adding the sum of the products of the maximal perpendicular diameters of measured lesions (SPD).

Response is based on CT alone or the CT component of PET/CT or MRI where applicable and the PET.

PET/CT scans are required at baseline for all patients with EMD.

- **M-protein:** synonyms include M-spike, monoclonal protein and myeloma protein, paraprotein, M-component.

Serum M-protein level is quantitated using densitometry on SPEP except in cases where the SPEP is felt to be unreliable.

- M-proteins migrating in the β -region (usually IgA M-proteins)
- Cases in which the M-spike is so large and narrow on agarose (some specimens >4 g/dL) that they underestimate the actual immunoglobulin level (by greater than 1500 mg/dL) due to technical staining properties of the agarose gel
- Cases in which there are multiple peaks of same monoclonal protein (aggregates or dimers)

If SPEP is not available or felt to be unreliable (above examples) for routine M-protein quantitation, then quantitative immunoglobulin levels derived from nephelometry or turbidometry can be accepted. However, this must be explicitly reported at baseline, and only nephelometry can be used for that patient to assess response. SPEP derived M-spike values and quantitative nephelometric immunoglobulin values cannot be used interchangeably.

Urine M-protein measurement is estimated using 24-h UPEP only. Random or 24 h urine tests measuring kappa and lambda light chain levels are not reliable and are not recommended.

- **FLC estimation** is currently carried out using the serum FLC assay (Freelite, The Binding Site Limited, UK). Patients with kappa/lambda FLC ratio <0.26 are defined as having monoclonal lambda FLC and those with ratios >1.65 as having a monoclonal kappa FLC. The monoclonal light chain isotype is considered the involved FLC isotype, and the opposite light chain type as the uninvolved FLC type.
- **CT, PET/CT or MRI** should be performed on all patients with EMD at baseline. This should be repeated after 1 cycle and then every three cycles or more frequently if clinically indicated. The same modality should be used for serial assessment.

- **Peripheral blood testing for circulating plasma cells** should be performed in all patients with plasma cell leukemia at baseline and after 1 cycle and every two cycles thereafter. Peripheral smear or flow cytometry may be used to evaluate circulating plasma cells, but the same modality should be used throughout the study.
- **Response terms:** The following response terms will be used to define M protein response: stringent Complete Response (sCR), complete response (CR), very good partial response (VGPR), partial response (PR), Minimal Response (MR), stable disease (SD), and progressive disease (PD). EMD or PCL response definitions/criteria are detailed below.

In addition, for each response category, there will be an “unconfirmed” response category, which will be for internal use, for the purpose of guiding decision making and test ordering. These designations will be applied at the time of the first measurement at which the quantitative aspect of the response category has been satisfied without the confirmation step having been satisfied. The designation “u” will precede the standard abbreviations, and will include usCR, uCR, uVGPR, uPR, uMR, uPD.

- **Measurable disease:** Patients who have a measurable serum or urine M-protein.
 - Serum M-protein ≥ 1 g/dl
 - Urine M-protein ≥ 200 mg/24 h
 - Serum FLC assay: Involved FLC level ≥ 10 mg/dl provided serum FLC ratio is abnormal
 - At least one plasmacytoma that has a single diameter of ≥ 2 cm.
 - Plasma cell count exceeding 500/microL or 5 percent of the peripheral blood white cells

The serum free light chain (FLC) assay is of particular use in monitoring response to therapy in patients who have oligo-secretory or non-secretory disease and **should be used in assessing response only if the baseline serum and/or urine M proteins are not “measurable” as above, and the baseline level of the involved FLC is “measurable.”** When using this assay, it is important to note that the FLC levels vary considerably with changes in renal function and in patients with renal insufficiency, the levels of both the kappa and lambda may remain elevated, but the ratio normalizes with achievement of CR. Thus, both the level of the involved and the uninvolved FLC isotype (i.e., the involved/uninvolved ratio or involved-uninvolved difference) should be considered in assessing response. ***Patients included on the study on the basis of FLC alone (i.e., no measurable serum/urine m-spike) should be the only ones who are evaluated using FLC response criteria. The others should follow usual criteria and ignore FLC results*** with the exception of defining stringent complete response.

- **Evaluable disease:** Patients who do not have a “measurable” serum M-spike, serum free light chain, or urine M-spike.
- **Oligosecretory myeloma:** Patient with multiple myeloma who has NEVER had “measurable” serum M-spike or urine M-spike, but has had a detectable monoclonal protein in his/her serum and/or urine and/or measurable serum free light chain.
- **Non-secretory myeloma:** Patient with multiple myeloma who has NEVER had a detectable monoclonal protein in his/her serum and/or urine.

11.2 Clarification of test indications

Listed below are the minimal required tests required to assess response based on the characteristics of their disease at on study.

Table 11.2				
Tests Required To Assess M protein Response (Must Be Done At Each Disease Measurement Visit except as indicated^{1,2})				
On Study Baseline Value	SPEP	24 hr UPEP²	Ig FLC	BM Bx
Serum M-spike \geq 1 g/dl, and urine M-spike \geq 200 mg/24 hrs	X	X		
Serum M-spike \geq 1 g/dl, but urine M-spike $<$ 200 mg/24 hrs	X			
Serum M-spike $<$ 1 g/dl, and urine M-spike \geq 200 mg/24 hrs		X		
Serum M-spike $<$ 1 g/dl, urine M-spike $<$ 200 mg/24 hrs, but involved Ig FLC is \geq 10 mg/dL			X	

¹ **Immunofixation studies of both serum and urine** are required to document CR regardless of registration values, and in addition **FLC measurement and bone marrow immunophenotyping** is required to document sCR. SPEP and UPEP are required to document VGPR regardless of registration values.

² For serum measurable patients, 24 hour urine does not need to be confirmed (i.e. repeated after documented response) for any response category

³ Bone marrow biopsy results do not need to be confirmed (i.e. repeated after documented response).

11.3 Confirmed response

In order to be classified as an M protein response, confirmation of serum monoclonal protein, serum immunoglobulin free light chain (when primary determinant of response) and urine monoclonal protein (when primary determinant of response) results must be made by verification on two consecutive determinations.

- Bone marrow aspirate and biopsy are **only** required to document CR or sCR, except for patients with evaluable disease **only**, where a bone marrow is required to document all response categories including progression. However, a second confirmatory bone marrow is **not** required to confirm response in any case.
- Radiographic studies are not required to satisfy these response requirements; however, if radiographic studies were performed there should be no evidence of progressive or new bone lesions.

Appropriate tests required to document and confirm response are listed in Table 11.2

11.4 Bone progression:

Caution must be exercised to avoid rating progression or relapse on the basis of variation of radiologic technique alone. Compression fracture does not exclude continued response and may not indicate progression. When progression is based on skeletal disease alone, it should be discussed with the Study Chair before removing the patient from the study.

11.5 Response and Progression:

Criteria for response and progression are listed in Table 11.5. Progressive disease for all patients as defined in Table 11.5. Although the definition for “relapse from CR (or sCR)” is listed, this will be documented as a response category in ONLY those protocols evaluating disease free survival.

CATEGORY	RESPONSE CRITERIA ^a
Stringent complete response (sCR)^e	
 • CR as defined below plus all of the following: • Normal serum FLC ratio • Absence of clonal cells in bone marrow by immunohistochemistry or immunofluorescence ^b • Not applicable for those patients who do not have a “measurable” serum M-spike, serum free light chain, or urine M-spike at baseline
Complete response (CR)	
 • Negative immunofixation of the serum and urine • <5% plasma cells in bone marrow • If at on study, the only measurable non-bone marrow parameter was FLC, normalization of FLC ratio • For patients with extramedullary plasmacytoma present at baseline: a) FDG-avid or PET positive prior to therapy: Mass of any size permitted if PET negative and b) Variably FDG-avid or PET negative: Regression to normal size on CT. For patients with only skin involvement, these same criteria apply to skin lesions measured with a ruler. • For patients with plasma cell leukemia at baseline, complete absence of circulating plasma cells
Very good partial response (VGPR)^e	
 • PR as defined below plus all of the following: • Serum and urine M-component detectable by immunofixation but not on electrophoresis or • If at on study, serum measurable, $\geq 90\%$ or greater reduction in serum M-component plus urine M-component <100 mg per 24 h • If at on study, the only measurable non-bone marrow parameter was FLC, $\geq 90\%$ or greater reduction in the difference between involved and uninvolved free light chain levels • Not applicable for those patients who do not have a “measurable” serum M-spike, serum free light chain, or urine M-spike at baseline

Table 11.5	
CATEGORY	RESPONSE CRITERIA ^a
Partial Response (PR)	
 • One of the following: 
 ▪ If at on study, serum and urine measurable, a $\geq 50\%$ reduction of serum M-protein and reduction in 24-h urinary M-protein by $\geq 90\%$ or to < 200 mg per 24 h ▪ If at on study, only serum measurable (but urine not), a $\geq 50\%$ reduction of serum M-protein ▪ If at on study, urine measurable (but serum not), a reduction in 24-h urinary M-protein by $\geq 90\%$ or to < 200 mg per 24 h ▪ If at on study, the only measurable parameter was FLC, a $\geq 50\%$ decrease in the difference between involved and uninvolved FLC levels ▪ For patients with extramedullary plasmacytoma present at baseline: $\geq 50\%$ decrease in SPD of up to 6 largest dominant masses and a) FDG-avid or PET positive prior to therapy: one or more PET positive at previously involved sites OR b) Variably FDG-avid or PET negative: regression on CT or by measurements with a ruler in patients with only skin involvement ▪ For patients with plasma cell leukemia at baseline, $\geq 50\%$ reduction in the circulating plasma cell count
Stable disease (SD)	Not meeting criteria for sCR, CR, VGPR, PR, or progressive disease
Progressive disease (PD) ^d	
Any one or more of the following:
 
 • Increase of 25% from lowest value in ^f 
 ▪ Serum M-component (absolute increase must be ≥ 0.5 g/dl)^c ▪ Serum M-component increase ≥ 1 g/dl, if lowest M component was ≥ 5 g/dl ▪ Urine M-component (absolute increase must be ≥ 200 mg/24 h)^c ▪ If at on study, the only measurable parameter was FLC, the difference between involved and uninvolved FLC levels (absolute increase must be > 10 mg/dl)^c ▪ Bone marrow plasma cell percentage (absolute % must be $\geq 10\%$)^c ▪ Appearance of a new lesion(s), $\geq 50\%$ increase from nadir in SPD of more than one lesion, or $\geq 50\%$ increase in longest diameter of a previous lesion > 1 cm in short axis. Lesions PET positive if PET positive prior to therapy ▪ $\geq 50\%$ increase in circulating plasma cells (minimum of 200/mcl) 
Or any one or more of the following felt related to the underlying clonal plasma cell proliferative disorder
 
 ▪ Hypercalcemia (≥ 11.5 mg/dl) if considered related to myeloma ▪ Decrease in hemoglobin of ≥ 2 g/dl if considered related to myeloma ▪ Serum creatinine level ≥ 2 mg/dl if considered related to myeloma

^a All response categories require two consecutive assessments made at anytime before the institution of any new therapy; complete and PR, MR and SD categories also require no known evidence of progressive or new bone lesions if radiographic studies were performed. Radiographic studies are not required to satisfy these response requirements. Bone marrow assessments need not be confirmed. Each category, except for stable disease, will have a working subcategory of “unconfirmed” [prefix ‘u’] to designate first time point at which response category MAY have been achieved if confirmed.

^b Presence/absence of clonal cells is based upon the k/λ ratio. An abnormal k/λ ratio by immunohistochemistry and/or immunofluorescence requires a minimum of 100 plasma cells for analysis. An abnormal ratio reflecting presence of an abnormal clone is k/λ of $>4:1$ or $<1:2$.

^c Positive immunofixation alone in a patient previously classified as CR will not be considered progression.

^d Progressive disease should be confirmed. However, treatment may be discontinued for progressive disease that is unconfirmed per physician discretion. In this case, an objective status of PD should be entered on the measurement form and progressive disease should be reported on the event monitoring form.

^e Does not apply to EMD or PCL

^f In the case where a value is felt to be a spurious result per physician discretion (for example, a possible lab error), that value will not be considered when determining the lowest value.

11.6 Types of Response:

11.61 Biochemical response will be defined as detailed above for serum, urine, and FLC.

11.62 Extramedullary disease response will be defined as detailed above for plasmacytomas and plasma cell leukemia.

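### Read literally, the plasmacytoma PR criterion in Table 11.5 can score a PET-negative patient SD where the same patient with residual uptake would be PR

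*Combined protocol and SAP*

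**What the plan says.** Table 11.5 (section 11.5) grants PR if any one of several routes is met: the biochemical routes (serum, urine or FLC), a plasmacytoma route and a PCL route. The plasmacytoma route asks for an SPD fall of at least 50% *and* a PET condition with two limbs joined by *or*:

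- Limb (a): "FDG-avid or PET positive prior to therapy: one or more PET positive at previously involved sites".
- Limb (b): "Variably FDG-avid or PET negative: regression on CT or by measurements with a ruler", the ruler being for patients with only skin involvement.

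The other rows that matter are these:

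- **CR.** For lesions avid before therapy, "Mass of any size permitted if PET negative". For the rest, "Variably FDG-avid or PET negative: Regression to normal size on CT". CR also lists "Negative immunofixation of the serum and urine" and marrow plasma cells below 5%.
- **VGPR.** It builds on PR, and footnote e to the sCR and VGPR rows says "Does not apply to EMD or PCL".
- **SD.** "Not meeting criteria for sCR, CR, VGPR, PR, or progressive disease".
- **PD.** The lesion item includes "Lesions PET positive if PET positive prior to therapy".

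Section 16.311 counts a success when the objective status is sCR, CR, VGPR or PR at two consecutive evaluations. Section 16.2 stops the trial at 2 or fewer successes in 10 and calls the regimen promising at 10 or more in 27.

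**The concern.** A response scale should not move a patient down when the disease improves. Limb (a) appears to do that: losing the last PET-positive site removes the PR, and unless every other CR item is met there is nothing above SD to move to. SD is not a success under 16.311, so the classification feeds directly into the 2/10 and 9/27 rules. Even if the trial team applies the bullet more generously, the text does not say so, and two scorers could put the same patient in different categories. Sections 11.62 and 16.321 can also be read to count this patient as an extramedullary responder, because the plasmacytoma line of CR is met, while the overall status is SD.

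**Working it through.** **1. The plan's own figures.** With p the probability of a scored success:

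- P(interim stop) = P(Bin(10, p) ≤ 2)
- P(promising) = Σ over x = 3 to 10 of P(Bin(10, p) = x) × P(Bin(17, p) ≥ 10 − x)

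At p = 0.50 the interim stop is (1 + 10 + 45)/1024 = 0.0547. For p = 0.25, 0.30, 0.35, 0.40, 0.45 and 0.50, P(promising) is 0.0994, 0.2428, 0.4387, 0.6392, 0.7999 and 0.9036. The interim stop is 0.526, 0.383, 0.262, 0.167, 0.100 and 0.055. Both rows of the table in 16.24 are reproduced.

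**2. Table 11.5 as a decision table.** Take a patient avid at baseline, with SPD down at least 50%, no PCL and no PD, and apply the literal wording at one evaluation:

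| All lesions PET negative | Other CR items met | Biochemical PR | Status |
|---|---|---|---|
| yes | yes | yes or no | CR |
| yes | no | yes | PR |
| yes | no | no | **SD** |
| no | yes or no | yes or no | PR |

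Of the eight combinations, exactly one is SD. With one site still PET positive, the same patient is PR.

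**3. Does limb (b) rescue the patient?** Only if PET negative there means follow-up status. In the CR row the same split works only as baseline status. Otherwise a PET-negative mass would be allowed at any size by (a) and required to be of normal size by (b). The PD row also refers to PET status before therapy. The baseline reading is therefore the more natural one for PR. The PR row does not settle it, because limb (b) names no time point there.

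**4. Can the SD cell occur?** Yes. Section 11.1 does not require an M-spike for entry, and 12.1 lists extramedullary disease as the only followed parameter for some patients. Without PCL, the plasmacytoma route is their only way to PR. CR could fail on marrow of 5% or more, or on immunofixation of a non-measurable protein. In a patient with measurable serum M-protein that falls by less than 50%, remaining protein would be expected to keep immunofixation positive, so one fact both denies biochemical PR and fails CR. Objective 2.22 sets out to study biochemical versus extramedullary discordance.

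**5. From one evaluation to the endpoint.** The SD cell describes a single evaluation. Footnote a to Table 11.5 lets the two consecutive assessments fall at any time before new therapy. A patient with two PRs before turning PET negative is already a success, and so is one who later has two consecutive CRs. Failure needs the SD status to block every such pair.

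**6. Illustration of size.** Let f be the share of true responders lost in this way. It is an assumption, since the documents give no value. The scored rate is p = true rate × (1 − f), with patients independent.

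| f | p at true 0.50 | Promising | Interim stop | Fall in P(promising) | Expected lost in 27 (27 × 0.5 × f) | Promising at true 0.25 |
|---|---|---|---|---|---|---|
| 0 | 0.500 | 0.904 | 0.055 | – | 0 | 0.099 |
| 2% | 0.490 | 0.887 | 0.062 | 0.016 | 0.27 | 0.089 |
| 5% | 0.475 | 0.859 | 0.075 | 0.045 | 0.68 | 0.075 |
| 10% | 0.450 | 0.800 | 0.100 | 0.104 | 1.35 | 0.055 |

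The gap can only remove successes, so the fall in P(promising) is the probability that it changes the trial's decision. Power stays at 0.85 or more until f is about 5.8%.

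**The case against.** The best defence is that the PR bullet is loosely worded rather than wrong. Limb (b) has no time point in the PR row and is an alternative to (a), so a patient who has regressed on CT and is now PET negative fits its words. Section 11.1 allows response to be judged on CT alone. If limb (a) were mandatory, CT alone could never document a plasmacytoma PR in a baseline-avid patient. On that view the SPD fall is the real test, and residual uptake only marks what separates PR from CR.

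The defence can add that the subgroup is narrow, that the shares in the illustration have no source, and that the error is conservative. Section 13.1 continues treatment for SD and PR alike, so this status by itself does not change treatment.

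Most of this stands and limits the size of the point. It does not remove it. The lenient reading is an inference that no section states, the parallel CR row points the other way, and the tension with 11.1 is itself a reason to clarify the bullet.

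**Conclusion.** The point holds as a gap in a primary-endpoint definition, of minor to moderate severity. It rests on the literal reading of limb (a) and on treating the CR items as jointly required. How often it occurs is unknown and probably low. The direction is conservative: some loss of power and a lower type I error.

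Three stronger conclusions might be inferred, and the documents do not support them:

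- **That PET-negative patients in general are scored SD.** Those who meet the other CR items are CR, and those with a biochemical PR are PR.
- **That every patient who reaches this status fails the primary endpoint.** Any pair of consecutive responding evaluations, before or after, is enough.
- **That the trial's power is really 0.80.** That figure belongs to an assumed 10% share. The figures in 16.24 are correct for the rule they describe, and the gap cannot create a false promising result.

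**What to change.** In the plasmacytoma bullet of the PR row, state two things:

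- An SPD fall of at least 50% over the largest masses (at most six), or by ruler where only skin is involved, is PR whenever overall CR is not met.
- PET positivity remaining at earlier sites is permitted but not required, and the rule also applies when no follow-up PET is available.

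This changes one bullet and needs no new scans, visits or patients.

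The drawback is that the change can only add responders, and section 7.4 shows that the text is already at Addendum 7 or later, so patients may have been scored. If so, rescore from the existing measurements and report the primary result, with the counts against the 2/10 and 9/27 rules, under both the current and the revised wording. Dual reporting makes any added responders visible.

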3.0 Patient Eligibility

3.1 Registration - Inclusion Criteria

- 3.11 Age ≥ 18 years.
- 3.12 Previously treated myeloma, currently with extramedullary disease (defined as plasmacytoma outside bone marrow that is not contiguous with a bone lesion) with at least one lesion that has a single diameter of ≥ 2 cm or plasma cell leukemia (defined as circulating plasma cells exceeding 5% of peripheral blood leukocytes or $0.5 \times 10^9/L$ or 200 cells/150000 events by flowcytometry).
- 3.13 The following laboratory values obtained ≤ 14 days prior to registration.
- Calculated creatinine clearance (using Cockcroft-Gault equation below)* ≥ 30 mL/min
 - Absolute neutrophil count (ANC) $\geq 1000/mm^3$
 - Platelet count $\geq 50,000/mm^3$
 - Hemoglobin ≥ 8.0 g/dL

*Cockcroft-Gault Equation:

$$\text{Creatinine clearance for males} = \frac{(140 - \text{age})(\text{actual body weight in kg})}{(72)(\text{serum creatinine in mg/dL})}$$

$$\text{Creatinine clearance for females} = \frac{(140 - \text{age})(\text{actual body weight in kg})(0.85)}{(72)(\text{serum creatinine in mg/dL})}$$

- 3.14 Patients with measurable disease defined as at least one of the following:
- For patients with EMD measurable disease by CT or MRI or the CT portion of the PET/CT: Must have at least one lesion that has a single diameter of ≥ 2 cm. Skin lesions can be used if the area is ≥ 2 cm in at least one diameter and measured with a ruler.
 - Plasma cell count $\geq 0.5 \times 10^9/L$ or 5 percent of the peripheral blood white cells
 - Plasma cell count if determined by flow cytometry, $\geq 200/150,000$ events
- 3.15 ECOG performance status (PS) 0, 1 or 2 ([Appendix I](#)).
- 3.16 Provide informed written consent.
- 3.17 Negative pregnancy test done ≤ 7 days prior to registration, for women of childbearing potential only.
- 3.18 All study participants must be registered into the mandatory POMALYST REMS™ program, and be willing and able to comply with the requirements of the POMALYST REMS™ program.
- 3.19a Willing to return to enrolling institution for follow-up (during the Active Monitoring Phase of the study).
- 3.19b Willing to provide bone marrow and blood samples for correlative research purposes (see Sections 6.12 and 14.1).

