13.0 Treatment/Follow-up Decision at Evaluation of Patient

13.1 Patients who are sCR, CR, VGPR, PR, or SD (or usCR, uCR, uVGPR, uPR) will continue treatment per protocol.

13.2 Patients who develop progressive disease while receiving therapy will go to the event-monitoring phase.

13.3 Patients who go off protocol treatment for reasons other than PD will go to the event-monitoring phase per Section 18.0.

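### Table 11.5 counts myeloma-related creatinine and calcium as progression by absolute level, so an eligible patient can meet PD at the first on-study evaluation with no change from baseline

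*Combined protocol and SAP*

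**What the plan says.** The progression row of Table 11.5 (Section 11.5) has two routes.

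- **Disease-measure route.** M-protein, FLC difference and marrow plasma cells are judged as a rise from the lowest value. Lesions are judged by new appearance or growth, and circulating plasma cells by a percentage increase.
- **Clinical route.** It opens with "Or any one or more of the following felt related to the underlying clonal plasma cell proliferative disorder" and lists three items: "Hypercalcemia (≥ 11.5 mg/dl) if considered related to myeloma", "Decrease in hemoglobin of ≥ 2 g/dl if considered related to myeloma" and "Serum creatinine level ≥ 2 mg/dl if considered related to myeloma". Only the haemoglobin item is a change.

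The renal entry limit in Section 3.13 is "Calculated creatinine clearance (using Cockcroft-Gault equation below)* ≥ 30 mL/min". The other laboratory limits there are neutrophils, platelets and haemoglobin. There is no ceiling on serum creatinine, and neither Section 3.1 nor Section 3.2 limits calcium. The test schedule (Section 4.0) has both measured at baseline and before each 28-day cycle.

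On consequences, Section 13.2 says "Patients who develop progressive disease while receiving therapy will go to the event-monitoring phase". Section 16.322 dates PFS from registration to the first documented progression or death. Section 16.311 requires PR or better as the objective status at two consecutive evaluations, and every eligible treated patient who is not a major violation stays in the denominator. Footnote d to Table 11.5 asks for PD to be confirmed but lets treatment stop on unconfirmed PD. The schema says that confirmation is not required.

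**The concern.** A progression criterion should detect worsening after entry. A level that an eligible patient may already exceed at registration records the entry state instead. If that patient's renal impairment is due to myeloma, the attribution condition is met before the first dose and is still met a cycle later, even if plasmacytomas and M-protein are stable or shrinking.

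Two endpoints are exposed. PFS would gain an event about one cycle after the start of treatment that reflects no progression. The confirmed response rate could lose a responder, who would remain in the denominator as a failure. Sites could also diverge: one that applies the table literally and one that discounts a known baseline value would record different statuses from the same facts. With a cut-off of 10 successes in 27, one or two misrated patients can decide the result.

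**Working it through.** **1. The plan's own design figures.** The inputs are in Sections 16.21-16.24: stop if 2 or fewer of the first 10 respond, declare promising if at least 10 of 27 respond, null rate 25%, target rate 50%. With b the binomial probability,

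P(promising) = sum over x = 3 to 10 of b(x; 10, p) × P(Y ≥ 10 − x), where Y is binomial(17, p).

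This gives 0.0994 at p = 0.25 and 0.9036 at p = 0.50. The probability of stopping at the interim is 0.5256 and 0.0547. The plan states 0.10, 0.90, 0.53 and 0.05, so its figures reproduce.

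**2. Can an eligible patient already be at the creatinine level?** The protocol's equation is clearance = (140 − age) × kg / (72 × creatinine), multiplied by 0.85 for women. Setting clearance to 30 gives the highest eligible creatinine, (140 − age) × kg / 2160, again multiplied by 0.85 for women. Ages and weights below are examples.

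| Patient | Clearance at 2.0 mg/dl | Highest eligible creatinine |
|---|---|---|
| Man, 65 y, 80 kg | 75 × 80 / 144 = 41.7 | 6000 / 2160 = 2.78 |
| Man, 70 y, 70 kg | 70 × 70 / 144 = 34.0 | 4900 / 2160 = 2.27 |
| Woman, 65 y, 70 kg | 75 × 70 × 0.85 / 144 = 31.0 | 4462.5 / 2160 = 2.07 |
| Woman, 70 y, 70 kg | 70 × 70 × 0.85 / 144 = 28.9 | 4165 / 2160 = 1.93 |

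At exactly 2.0 mg/dl, a man is eligible when (140 − age) × kg is at least 72 × 2 × 30 = 4320, that is, from 57.6 kg at age 65 or 61.7 kg at age 70. A woman needs 4320 / 0.85 = 5082, that is, 67.8 kg at age 65. The first three patients in the table can enter at or above the PD level. The fourth cannot.

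**3. Calcium.** No arithmetic applies. The clearance limit says nothing about calcium, so this half rests only on the absence of any calcium limit at entry.

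**4. Does another provision close the gap?** Footnote d does not, because an unchanged abnormal value confirms itself on repeat, and the schema waives confirmation in any case. Footnote f sets aside spurious values only when the lowest value is determined. No footnote exempts a value present at baseline.

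**5. Illustrative effect on the primary decision.** Assume that k of 27 patients meet PD on their baseline value and that PD prevails over PR. A true 50% rate is then scored as 0.50 × (27 − k) / 27. Putting this rate into the formula of step 1:

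| k | Scored rate | Power |
|---|---|---|
| 0 | 0.500 | 0.904 |
| 1 | 0.481 | 0.872 |
| 2 | 0.463 | 0.832 |
| 3 | 0.444 | 0.785 |

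If instead exactly k patients are certain failures, placed at random among the 27, and the others respond at 50%, power is 0.88, 0.84 and 0.80 for k = 1, 2 and 3. The loss is slightly smaller and points the same way. The error only removes successes, so it does not raise the false-positive rate.

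**The case against.** The strongest reply is that these items call for judgement. Attribution to myeloma is stated both in the header and in each item, and Section 13.2 speaks of patients who develop progression. A sensible investigator would not call a stable, known creatinine progression. This stands in part: a raised value from another cause is not PD, and a reader who infers that any creatinine of 2 mg/dl triggers PD goes beyond the text. But attribution does not exclude impairment that was myeloma-related at entry. Section 11.5 makes Table 11.5 the definition of progression for all patients, and the table contains no requirement that the finding be new. Section 11.1 discusses FLC assessment in renal insufficiency, so such patients are foreseen.

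A reader might also infer that an affected patient cannot be credited with a response. The documents do not say so. Only stable disease is defined as excluding PD. PR requires one of its listed items, and footnote a bars response only for progressive or new bone lesions. A patient who meets both PR and PD fits Section 13.1 (continue) and Section 13.2 (event monitoring) alike. Loss of the response is therefore a possible result of a missing precedence rule, not a stated one.

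Three further limits stand. Eligibility at 2 mg/dl or more depends on age, weight and sex. Nothing in the documents suggests that calcium of 11.5 mg/dl or more would persist unchanged on study, and Section 3.24 allows bisphosphonates. The count of 1 to 3 patients has no source in the documents.

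**Conclusion.** The point holds in a limited form. Two of the three clinical progression items are levels with no baseline reference, and the entry criteria admit patients who may already be at those levels for myeloma-related reasons. Followed literally, the table gives such a patient a PFS event without progression. This is a stated rule that misfires, not merely missing detail. The effect on the primary endpoint is conditional: it needs PD to prevail over PR, which the plan leaves open.

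The creatinine half is well supported by the protocol's own equation. The calcium half is weaker. How many patients would be affected cannot be derived from the documents. On the assumption of 1 to 3 of 27 with PD prevailing, power at a true 50% rate falls from 0.90 to about 0.87-0.78. If no such patient enrols, nothing changes.

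**What to change.** For endpoint rating, reconcile the creatinine and calcium items of Table 11.5 with the entry criteria, so that they count as progression only when new or worsened relative to the patient's own baseline. The sponsor should set how worsening is judged in patients already at or above the level at entry. Simply dropping the items for them would leave real deterioration uncounted, for example a myeloma-related rise from 2.1 to 5 mg/dl. The plan should also state which status prevails when PR and PD criteria are both met. How the reconciled rating bears on stopping treatment under Section 13.2 is for the sponsor to decide.

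The cost is an edit to two items of the table and one sentence on precedence. No new data are needed, since both values are already collected at baseline and every cycle. The small downside is that progression by these items may be recorded later in patients with abnormal baseline values.
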